Finally, transplant glomerulopathy (TG), defined by double contouring of the glomerular basement membrane (GBM), is the most plausible and reliable of surrogate markers for poor outcomes in kidney transplantation. Early evidence of transplant glomerulopathy can be identified by electron microscopy (EM) when contouring of the GBM is associated with evidence of endothelial swelling (Haas 2014); however, long-term association with early graft loss has not been demonstrated with such early changes. Despite treatment with plasmapheresis and IVIg, TG evident by light microscopy (chronic glomerulopathy [cg] $\geq 1b$, ie, ≥ 1 glomerular capillaries with GBM double contours in 1 nonsclerotic glomerulus by light microscopy; EM confirmation recommended if available [Haas 2014]) has been associated with later formation of irreversible scarring observed on biopsy as interstitial fibrosis, glomerulosclerosis, and/or fibrointimal thickening (Montgomery 2010; Racusen et al. 1999) that eventually results in graft loss. Patients with TG on biopsy have greatly shortened graft survival compared with patients who have no evidence of TG (Sharif et al. 2014; Sun et al. 2012). Furthermore, TG on light microscopy has been universally accepted by transplant physicians and pathologists as a reliable surrogate marker of impending allograft loss.

Since TG, as described above, is indicative of poor graft survival, an effective treatment for AMR must modulate the underlying destructive host immune response that results in TG. Plasmapheresis, plasma exchange, or immune adsorption treatments and IVIg can decrease DSA titers; however, their use may not address the tissue destruction that occurs as a result of complement activation. Human leukocyte antigen-DSA complexes activate the classical pathway of the complement cascade, ultimately resulting in the formation of membrane attack complexes and continuous release of inflammatory cytokines and leukocyte infiltration (Levy and O'Donnell 2006).

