1.3.2 Clinical Experience with Antibody-mediated Rejection

One clinical study (0624-201) was conducted to assess the safety and effect of CINRYZE in the treatment of acute AMR in HLA-donor-sensitized kidney transplant recipients. Eighteen subjects with AMR were enrolled in the study and received an initial IV infusion of 5000 U of CINRYZE or placebo on Day 1, followed by 2500 U of CINRYZE or placebo IV on Days 3, 5, 7, 9, 11, and 13. All 18 subjects completed treatment and the study. Seven of 9 (78%) subjects who received CINRYZE and 6/9 (67%) who received placebo had a resolution of the qualifying episode of AMR based on clinical improvement of renal function and on classic Banff categorization of histopathology findings. The median number of days from the first dose of investigational product until AMR resolution was 20.0 days (range: 19 to 86 days) for subjects who received CINRYZE and 20.5 days (range: 20 to 22 days) for subjects who received placebo. All 7 (100%) subjects who received CINRYZE and had resolution of the qualifying episode had AMR resolution determined by histopathology.

Of the 6 subjects who received placebo and had resolution of the qualifying episode, 3 (50%) had AMR resolution based on clinical criteria and 4 (67%) had AMR resolution based on histopathology.

All 18 subjects had early protocol-mandated biopsies at Day 20; however, the 14 subjects from Johns Hopkins Medical Institute also had center-mandated biopsies 3-6 months after completion of investigational product therapy (n=7 CINRYZE; n=7 placebo). Since these 14 subjects had also been treated with the same standard of care regimen, the Central Pathologist read the long-term follow-up biopsies blinded to treatment assignment and determined the presence or absence of new TG by the published Banff criteria (Racusen et al. 1999; Sis et al. 2010). Of these 14 subjects, 3 of 7 placebo subjects had evidence of new TG as determined by double contouring of the GBM (cg \geq 1b; personal communication) with thickening of the PTC and ongoing PTC inflammation on histopathology. Notably, there were no new cases of Banff-qualified TG (cg \geq 1b; personal communication) with PTC inflammatory changes in the 7 subjects receiving CINRYZE (Montgomery et al. 2014).

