Based on available preclinical and clinical data, the levels of C1 INH sufficient for complement pathway inhibition elicited by antigen-antibody complexes are at least 100% above normal physiologic levels. Preliminary data from the pilot pharmacokinetic study 0624-100 demonstrated that following IV administration of 2000 U of CINRYZE in healthy subjects, the mean change from baseline in functional C1 INH activity was approximately 50-60%. Given that 1 U of C1 INH activity is found in 1 mL of plasma, to increase the functional activity of C1 INH by at least 100% (2-fold) in patients with acute AMR, a dose of ~5000 U will be required in an average adult. Given that CINRYZE has a half-life of ~60 hours in HAE patients and possibly shorter in patients with active inflammation such as AMR patients, subsequent doses of 2500 U given every other day are likely to maintain adequate functional C1 INH levels throughout the dosing period. Therefore, subjects randomized to the CINRYZE group in the randomized Phase 2 AMR pilot study (0624-201) received a loading dose of 5000 U (not to exceed 100 U/kg) followed by 2500 U (not to exceed 50 U/kg) every other day for a total of 7 doses. This regimen balanced the apparent dose-dependent nature of inhibiting complement activation elicited by antigen-antibody complexes, while minimizing the potential risk of coagulation observed in preclinical and clinical studies of C1 INH at doses ≥ 200 U/kg. In fact, in the pilot study 0624-201 in kidney transplant recipients with acute AMR, CINRYZE subjects achieved a mean C1 INH functional activity of 1.73 U/mL, near but not quite at twice the physiologic level for which we aimed. In the 0624-201 study, 14/18 subjects at a single site had a 6-month post-transplant allograft biopsy per center standard of care (n=7 CINRYZE; n=7 placebo). A lower incidence of new TG (cg \geq 1b with PTC inflammation) was observed in the CINRYZE cohort biopsies as compared to placebo (0 vs 43%, respectively) 3-6 months after initial AMR treatment (6 months post-transplant).

Balancing the risk of thrombotic events and the lower incidence of new TG observed in the CINRYZE cohort of the 0624-201 study, it is felt that 20,000 U given over 13 days is the optimal dosing regimen that maintains an appropriate balance between clinical requirements for replacement of endogenous C1 INH and the risk of AEs with a higher dose.

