Representative histopathology sections of each renal allograft biopsy (qualifying and all post-treatment biopsies) will be sent for processing to the investigative site's pathologist. Glass slides are required for Periodic acid Schiff, hematoxylin and eosin, trichrome and silver stains. If possible, glass slides for CD34 and CD68 must also be provided. The pathologist will process sections: (1) for hematoxylin and eosin stain and Periodic acid Schiff, trichrome, and silver stains and (2) for C4d presence by immunofluorescence (C4d images are required even if negative). If immunofluorescence images are not available, immunohistochemical glass slides must be provided instead. Whenever possible, sections will also be processed for immunoperoxidase stain for CD34 and CD68. Additionally, biopsy tissue remaining after the qualifying biopsy assessment should be preserved in paraffin or another method appropriate for EM processing. Electron microscopy images will be obtained locally for patients enrolled in the study. Biopsy tissue from the Month 6 biopsy will be also obtained for EM processing. Representative EM images obtained locally will be sent to the pathology EAC for determination of the presence of early GBM and/or endothelial damage not seen on light microscopy. This will be used for an exploratory analysis of long-term outcomes associated with such early changes seen only on EM.

Further details on glass slides and images required for submission to the pathology EAC will be provided in a separate document.

Biopsy slides and representative micrographs (including, but not limited to EM images) will be sent by the sites to the Sponsor's designee within 30 days after the biopsy, and will be provided to an independent, blinded pathology EAC for determination of the presence of new or worsening TG at 6 months of initiation of treatment. Furthermore, any additional biopsy that qualifies the subject for retreatment per protocol or that will be used to define AMR episode resolution will also be sent to the pathology EAC. Acute AMR confirmation will be according to published Banff criteria. These data will be recorded.

Electron Microscopy

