9.6 Sample Size Calculation and Power Considerations

A total of 112 subjects (56 CINRYZE, 56 Placebo) will be randomized in a 1:1 ratio into 2 treatment groups: CINRYZE or placebo. Sample size was calculated for the primary endpoint and the key secondary endpoint using nQuery Advisor 7.0.

The primary endpoint in the study is the proportion of subjects with new or worsening TG at 6 months after treatment initiation. A 43% absolute difference in TG at 6 months between treatment groups (3/7 in placebo and 0/7 in CINRYZE) was observed in a subset of subjects (14/18) in the completed randomized Phase 2 pilot study (0624-201). For this study, the assumed proportion of subjects with new or worsening TG at 6 months will be 50% in the placebo group and 10% in the CINRYZE group. A sample size of 60 subjects (30 in placebo and 30 in CINRYZE) would be needed to obtain at least 90% power to detect a significant treatment difference at an alpha level of 0.025 (1-sided test).

The key secondary endpoint in the study is the proportion of subjects with all-cause graft failure. Assuming the proportions of subjects with graft failure due to AMR are 64% and 25% for placebo and CINRYZE, respectively, and all-other-cause graft failure rate is 12% for both placebo and CINRYZE, then the proportions of subjects with all-cause graft failure are 68% and 34% for placebo and CINRYZE, respectively. A total of 100 subjects will provide 90% power to detect an absolute treatment difference of 34% at an alpha level of 0.025 (1-sided test) for all-cause graft failure. These assumptions are based on literature ([Haririan et al. 2009](#); [Sharif et al. 2014](#); [OPTN/STRT Annual Data Report 2012](#)). Considering a 10% drop-out rate during the study, 112 subjects will be randomized to the study. Under these assumptions, the expectation is that there will be approximately 34 all-cause graft failures on placebo and approximately 17 all-cause graft failures on CINRYZE, giving 51 events total. The trial will continue until 51 such events are accrued and adjudicated by the nephrology EAC unless stopped prematurely based on findings at an interim analysis or until the final subject enrolled has been followed for 4 years post initial treatment with investigational product.

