g3	Glomerulitis (mostly global) in more than 75% of glomerul

Criterion for allograft glomerulopathy

cg0	No GBM double contours by LM or EM
cg1	1a: no GBM double contours by LM but GBM double contours (incomplete or circumferential) in at least 3 glomerular capillaries by EM with associated endothelial swelling and/or subendothelial electronlucent widening 1b: ≥ 1 glomerular capillaries with GBM double contours in 1 nonsclerotic glomerulus by LM. EM confirmation is recommended if available.

cg2	Double contours affecting 26 to 50% of peripheral capillary loops in the most affected of nonsclerotic glomeruli
cg3	Double contours affecting more than 50% of peripheral capillary loops in the most affected of nonsclerotic glomeruli

Tubulitis score

T0	No mononuclear cells in tubules
T1	Foci with 1 to 4 cells/tubular cross section (or 10 tubular cells)
T2	Foci with 5 to 10 cells/tubular cross section
T3	Foci with > 10 cells/tubular cross section, or the presence of at least two areas of tubular basement membrane destruction accompanied by i2/i3 inflammation and t2 tubulitis elsewhere in the biopsy

Intimal arteritis score

V0	No arteritis
V1	Mild-to-moderate intimal arteritis in at least one arterial cross section
V2	Severe intimal arteritis with at least 25% luminal area lost in at least arterial cross section
V3	Transmural arteritis and/or arterial fibrinoid change and medial smooth muscle necrosis with lymphocytic infiltrate in vessel

Classification of peritubular capillaritis (PTC)

ptc0	No significant cortical ptc, or <10% of PTCs with inflammation
ptc1	≥ 10% of cortical peritubular capillaries with capillaritis, with max 3 to 4 luminal inflammatory cells
ptc2	≥ 10% of cortical peritubular capillaries with capillaritis, with max 5 to 10 luminal inflammatory cells
ptc3	≥ 10% of cortical peritubular capillaries with capillaritis, with > 10 luminal inflammatory cells

one comment on the composition (mononuclear cells vs. neutrophils) and extent (focal, ≤50% vs. diffuse, >50%) of peritubular capillaritis is recommended

Interstitial Inflammation score

i0	No or trivial interstitial inflammation
i1	10 to 25% of parenchyma inflamed
i2	26 to 50% of parenchyma inflamed
i3	More than 50% of parenchyma inflamed

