### 10.1 Primary Efficacy Endpoint(s) and Analysis

The primary efficacy endpoint is defined as the proportion of subjects with new or worsening TG at 6 months post-treatment as adjudicated by the pathology EAC based on 2013 Banff criteria (standard score). New or worsening TG at 6 months by the standard score is defined as an increase of 1 or more between qualifying biopsy and 6-month biopsy. Subjects who do not have the TG assessment at 6 months post-dose will be assigned as failures, i.e. having ‘new or worsening TG’.

The primary analysis specified below will be performed based on the FAS for the first and second interim analysis of this study. As a sensitivity analysis, the primary analysis will be also performed based on Per-protocol Analysis Set-1 in the second interim analysis of the study.

The primary endpoint will be presented as the proportion of subjects with new or worsening TG determined at 6 months, and their difference between treatments (  $\Delta_{Cinryze-Placebo}$  ) is defined as follows:

$$\Delta_{Cinryze-Placebo} = \Pi_{Cinryze} - \Pi_{Placebo}$$

where  $\Pi_{Cinryze}$  is the proportion of new or worsening TG at 6 months post treatment in the CINRYZE group and  $\Pi_{Placebo}$  is the proportion of new or worsening TG at 6 months post treatment in the placebo group.

The analysis will employ a type I error rate of 0.025 to test null hypothesis:

$$H_0 : \Pi_{Cinryze} - \Pi_{Placebo} \geq 0$$

Against the 1-sided alternative:

$$H_a : \Pi_{Cinryze} - \Pi_{Placebo} < 0$$

There will be two interim analyses to assess the primary endpoint.

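### Does the primary endpoint count glomerulopathy seen only on electron microscopy, against the light-microscopy surrogate the trial relies on?

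*SAP*

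**What the plan says.** SAP 10.1 takes the primary event from the pathology endpoint adjudication committee (EAC), using the 2013 Banff standard score. New or worsening TG "by the standard score is defined as an increase of 1 or more between qualifying biopsy and 6-month biopsy". SAP Appendix 2A then sets the analysed value from question 6 of the committee's final form: yes and insufficient data count as failure, no does not. Protocol 9.8.1 refers only to Banff criteria. Protocol 9.5.3.1 leaves the committee's rules to its charter.

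The scale is in protocol Appendix 2. Grade cg0 requires no double contours by light microscopy or EM. Grade cg1 has two parts. The first reads "1a: no GBM double contours by LM but GBM double contours (incomplete or circumferential) in at least 3 glomerular capillaries by EM"; the second, 1b, is the first grade visible by light microscopy.

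Protocol 1.2 bases the surrogate on the second part: "TG on light microscopy has been universally accepted by transplant physicians and pathologists as a reliable surrogate marker of impending allograft loss". Of the early EM findings it says "long-term association with early graft loss has not been demonstrated with such early changes". Protocol 7.2.2.2 gives EM findings not visible by light microscopy a separate role: "This will be used for an exploratory analysis of long-term outcomes associated with such early changes seen only on EM".

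**The concern.** Read on its own, the SAP sentence conflicts with the protocol's rationale. If the standard score is the integer grade, cg0 to cg1a is a rise of 1 and counts, though the protocol says such change has no shown link to early graft loss. On the same reading cg1a to cg1b, the first TG visible by light microscopy, is a rise of 0 and is missed.

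The pilot result cited for the sample size was a light-microscopy finding. Protocol 1.3.2 reports that "3 of 7 placebo subjects had evidence of new TG as determined by double contouring of the GBM" at cg 1b or above, and protocol 9.6 carries this forward as "A 43% absolute difference in TG at 6 months between treatment groups (3/7 in placebo and 0/7 in CINRYZE) was observed".

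Two further features add to the worry. EM is required at Month 6, but at the qualifying biopsy only if it was standard of care or tissue remained, so an EM-only lesion could look new for want of a baseline reading. The granular rule for new TG (cg 0 rising above 0) is equally silent on 1a.

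At stake is whether the reported primary result describes the surrogate the protocol defends or a mixture with a finding of unknown meaning.

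**Working it through.** **1. What each reading counts.** The grades are 0, 1a, 1b, 2 and 3, which gives 5 × 4 / 2 = 10 upward changes. The reference is a light-microscopy rule: 0 or 1a rising to at least 1b (2 × 3 = 6 changes), or at least 1b rising further (3 changes), 9 in all.

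| Change | Light-microscopy rule | Integer grade | Ordered steps | 1a treated as no TG |
|---|---|---|---|---|
| 0 to 1a | no | event | event | no |
| 1a to 1b | event | no | event | event |
| Other 8 | event | event | event | event |
| Total of 10 | 9 | 9 | 10 | 9 |

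The integer reading differs from the reference on 2 changes and the ordered-step reading on 1. Treating 1a as not yet TG differs on none.

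**2. Which reading the documents support.** Protocol 1.2 defines the surrogate by light microscopy. Protocol 7.2.2.2 and SAP 2.1 put change seen only on EM into exploratory analysis. SAP 20 lists TG evident only on EM as its own table (14.2.4.6.2), which makes little sense if such cases are already primary events. Against this, protocol 7.2.2.2 also sends EM images to the committee for the primary assessment. That has an ordinary explanation: Appendix 2 recommends EM confirmation of grade 1b where available. Taken together, the last column is the natural reading.

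**3. The design figure.** Inputs from protocol 9.6: 50% against 10%, one-sided 0.025, 90% power. The mean proportion is 0.30.

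n per arm = [1.960 × √(2 × 0.30 × 0.70) + 1.282 × √(0.25 + 0.09)]² / 0.40² = (1.270 + 0.747)² / 0.16 = 25.4, so 26.

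With continuity correction this is 31 per arm, or 62 in all, against the 60 stated. Exact one-sided Fisher power at 30 per arm is 91.4%, so the claim of at least 90% holds. The assumed rates are 50% and 10%, not the pilot's 43% and 0%, so the 1a question does not upset the calculation as stated.

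**4. What EM-only events would do, on an assumption.** The documents give no cg1a rate. Suppose a fraction q of light-microscopy-negative subjects in each arm has cg1a and is counted. The rates become 0.50 + 0.50q and 0.10 + 0.90q, and the difference is 0.40 × (1 − q).

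| q (assumed) | Placebo | CINRYZE | Fisher power, 30 per arm, one-sided 0.0249 |
|---|---|---|---|
| 0 | 50% | 10% | 91.4% |
| 5% | 52.5% | 14.5% | 84.5% |
| 10% | 55% | 19% | 76.9% |
| 20% | 60% | 28% | 62.6% |
| 30% | 65% | 37% | 49.5% |

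This shows that the rule would matter if the committee counted cg1a and cg1a were common. It is no evidence for either. If q differed between arms, the shift could go either way.

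**5. One subject.** At the planned 15 per arm, 1/15 = 6.7 percentage points. SAP 10.1 says balanced arms are assumed there for simplicity.

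**The case for a change.** The strongest case for a change is that the SAP states its own numeric rule. If the charter agrees with that rule taken literally, the mismatch with the surrogate is real; if it does not, the SAP misdescribes the analysed endpoint. Equal EM-only events in both arms would shrink a true difference, which is the unfavourable direction in a trial stopped for futility. The abbreviated report will still carry four TG tables (14.2.1.1a to d), none with a 1a/1b cut in its title. The Banff shift table (14.2.3.3.2) and both EM tables (14.2.4.6.1 and 14.2.4.6.2) are not being produced. A cross-tabulation of cg grades would need no new biopsies.

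Part of this stands. The sentence is incomplete, and a reader of the report would gain from seeing the rule. It does not show a defect in the analysis. The committee's answer determines the event, and a rule held in a charter is not absent from the trial. The table shells are a separate document, so their footnotes are unknown. Five listings with TG status, committee assessments and EM findings (16.2.6.1.1, 16.2.6.1.2a, 16.2.6.1.2b, 16.2.6.1.3 and 16.2.6.1.4) are being produced. The granular rule also has a worsening arm, a 6.25 rise in double-contour percentage, which does not depend on the grade label and could catch some cg1a-to-cg1b changes.

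**Conclusion.** No change to the plan. SAP 10.1 leaves a definitional gap that a literal reader could fill wrongly, but the protocol's light-microscopy surrogate and the exploratory role of EM-only change point to the sensible reading. The committee's recorded answer fixes the endpoint whatever the SAP sentence says.

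No effect on the result has been shown. Its size and direction cannot be estimated without a cg1a rate and the charter; the power losses tabulated above rest wholly on assumed rates. SAP 17 records that the sponsor stopped the study for futility after the first interim analysis and that the key secondary analysis will not be done. Rewording the event rule now would alter neither the classifications nor that decision, and would come after unblinded data were reviewed.

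What remains is a reporting courtesy: cite the charter's handling of cg1a and cg1b, for the standard and granular scores, in the abbreviated report. If the two were recorded separately, a descriptive cg shift table labelled post hoc is optional. This conclusion assumes that the charter contains a rule and that the committee applied it consistently and blinded, as protocol 9.5.3.1 provides.
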